## **6.5 Procedures**

### **Phase One: Observational Study**

Potential participants will be approached by a trained IRB-approved research assistant during their stay at GMC or GWV labor and delivery to inquire if the patient and their infant would be interested in enrolling in the research project. The research assistant will explain the study in-depth to the patient to ensure they understand the scope of the project. In addition, the patient will be given a packet containing an information sheet which explains the contents of the study packet, two copies of the consent form of which one will be signed and kept by the study team and the other the patient will sign and take home, a flyer outlining the WIC program and how to enroll, and information regarding signing up for MyGeisinger to assist in monitoring their child's care. Should the patient opt to sign-up for MyGeisinger during their stay in Labor and Delivery, each research assistant will be equipped with a Geisinger iPad on which the RA can enroll the patient in the MyGeisinger system.

Enrolled participants will be asked their preference for receiving survey packets, either by United States Postal Service or an emailed link to an electronic survey system, REDCap. Participant preference for hard versus electronic survey packets, respectively, will be obtained after consent and during the enrollment process. Participants completing survey packets electronically will be directed to the Pennsylvania State University's REDCap. Hard copy survey packets will be mailed to [name], Penn State University. Participants will complete an enrollment packet (Attachment 3) during the initial screening and recruitment into the research study followed by survey packets at 2 months (Attachment 4), 5 months (Attachment 5), and 7 months (Attachment 6), as well as a survey regarding patient perception of coordination of care and personalized care, corresponding with duration of study participation. Each mailed survey packet will be accompanied by a cover letter instructing the parent to return the survey using the pre-paid stamped envelope. If the mother/guardian is unable to complete the survey in the hospital, the survey packet will be distributed, per participant preference, and returned within one week. Parents that complete the 2, 5 and 7 month survey packets will receive a \$50 gift card for their

---

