## **Phase Two: Randomized Controlled Trial**

Procedures for Phase Two, Randomized Controlled Trial are the same as those for Phase One, Observational Study except that: 1) participants will be randomized to the treatment or control groups following participant consent/authorization/agreement. An electronic program will be used to randomly assign patients to a group; 2) Pediatric participant data will be extracted from their electronic health records and WIC records to document visit frequency, physical exam, and feeding or nutrition-related metrics 3) Pediatric participants will be given educational materials based on upon their recruitment in the intervention/control arm. These data will be electronically shared between WIC and Geisinger PCPs for the purpose of coordinating care for a 6 month intervention period and then disabled. Geisinger and WIC will share agreed upon data elements using a secure, File Transport Portal (FTP) site daily. Verification of shared participants between GHS and WIC will be authenticated with mother's name, mother's telephone number, date of birth, date of delivery, infant name, and birth date. To increase the likelihood of intervention arm participants enrolling in WIC, the mother's telephone number will be transferred. The telephone number will be used by WIC to contact the participant and schedule an initial visit with a WIC nutritionist in Luzerne County. Following authentication, random participant IDs will be assigned to protect confidentiality; and 3) Participants will be blind to group assignment, however PCPs and WIC will know group assignment because shared data for participants in the treatment group will be electronically displayed in the EHR at Geisinger and the QuikWIC

---

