system at WIC for the purpose of coordinating care. A trained research assistant or project coordinator will access the participating patient's medical record for the purposes of creating a documentation encounter in which the data collected from the QuikWIC system will be entered. This data will be stored in EPIC flowsheet rows. The data will then be displayed for the provider in the progress note to assist in the coordination of care. All participants will complete an informed consent form which will include PHI elements being shared. Throughout enrollment in the study, intervention participants will receive a phone call from a trained Geisinger nurse to assist with providing educational guidance for their child (feeding, sleep, tummy time, etc.) We anticipate this call will last around 10 minutes. To best serve the pediatric patient population enrolled in this RCT, the study team will be providing both intervention and control participants with educational materials that were developed in part by the AAP, but also vetted studies which were conducted at The Pennsylvania State University. Educational materials will be distributed to WIC for use during nutrition visits, as well as, provided during enrollment into the study and sent via mail. The purpose of the educational materials is to provide added value to parents enrolled in the study and assist them in providing care for their infant. To ensure participants are able to attend their scheduled WIC nutritionist appointments, the study team will provide a small business-size colored card at enrollment with the WIC contact information to reschedule their appointments if the need arises. The reschedule information is as follows: [name] or Toll free- [name]. In addition, during the 7 month enrollment period, the EHL survey (standard of care) will not fire for control participants, this will be sent via mail included in the 2,5,7 month survey packets. Post-enrollment, the study team will also mail a postcard to participants thanking them for participating in the study and a short high level overview of their participation. The post-card will also serve as a reminder that the participant will be receiving surveys at 3 time points throughout their enrollment. For intervention patients that do not complete the EHL screener at their regularly scheduled WCV, the study team will send a mailed copy of the EHL survey to the home for the parent to complete. To ensure that intervention participants are presented the opportunity to complete the EHL screener, the study team will include a paper copy of the screener in the participant's enrollment packet. The survey will only be included should the participant choose not to sign-up for MyGeisinger and prefer to complete the survey on paper Enrollment in MyGeisinger is not an inclusion/exclusion criteria. For participants that are given the EHL screener at enrollment, once the screener is completed at home, the participant will be asked if they could please bring the survey with them to their initial WIC visit. The screener will be used to better inform the WIC nutritionist visit and does not contain PHI. The screener will then be collected by the WIC nutritionist and transferred electronically back to Geisinger study staff. This data is essential in comparing intervention and control participants. To ensure that our participants are able to receive their survey packets in a timely manner, whether by mail or email as indicated by the participant, a study staff member will contact the participant via phone call. This phone call will consist of confirmation of receipt of survey, and to allow the participant to ask any questions that have arisen through the process of reading the questionnaire and answering the questions to the best of their ability. If the study team is unable to reach the participant via phone, a voicemail will be left asking the participant to call the study team back if they did not receive their survey. Participants will also receive an

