
---

completed survey, they will be enrolled into the study and care will resume as noted above based upon whether the participant is randomized to the intervention or control arm.

To ensure providers are effectively utilizing the coordination of care display module that was built within EPIC, the study team plans to conduct physician shadowing at participating clinics in Luzerne County. This will include shadowing providers, ensuring the IT module is working as intended, and to provide any oversight/problem solving that is necessary. The study team will also use this opportunity to discuss physician satisfaction with the end product and improvements/modifications that should be made to improve efficiency and assist with current workloads.

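### On the in-hospital route of the RCT, randomisation and arm-dependent items may come before a late-returned enrollment survey, so some survey baselines can be post-allocation

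*Protocol*

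**What the plan says.** The order of events has to be assembled from several parts of the protocol.

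- **Carry-over (Section 6.5, Phase Two).** "Procedures for Phase Two, Randomized Controlled Trial are the same as those for Phase One, Observational Study except that" a list of changes applies. None of the changes alters when the enrollment survey is completed.
- **Randomisation (Section 6.5, Phase Two).** "participants will be randomized to the treatment or control groups following participant consent/authorization/agreement". Consent is the only stated condition.
- **Enrollment survey (Section 6.5, Phase One).** The normal course is that "Participants will complete an enrollment packet (Attachment 3) during the initial screening and recruitment into the research study". The fallback reads: "If the mother/guardian is unable to complete the survey in the hospital, the survey packet will be distributed" by the means she prefers, with return due within one week.
- **Arm-dependent items (Section 6.5, Phase Two).** For intervention participants, "the study team will include a paper copy of the screener in the" enrollment packet, but only if they do not sign up for MyGeisinger. Educational materials go to both arms, but according to arm, and are "provided during enrollment into the study and sent via mail". For the intervention arm the mother's telephone number also goes to WIC so that a first visit can be booked. No earliest date is given for this.
- **Newborn-visit and prenatal route (Section 6.5, Phase Two).** Once the participant has returned the consent and the "completed survey, they will be enrolled into the study and care will resume as noted above based upon whether the participant is randomized" to intervention or control.

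**The concern.** A baseline measurement should be fixed before allocation can influence it. If it is taken afterwards, three things can go wrong. Any early effect of arm-dependent material enters the baseline and is subtracted from the change. A covariate or moderator taken from that survey is no longer guaranteed to be independent of arm. Failure to return the baseline can also differ by arm.

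Section 6.6.1 relies on such measurements. It analyses changes in survey subscales by repeated analysis of variance and tests survey variables as moderators and mediators. It also uses initial feeding mode intent and its interaction with study group as model effects. Because the newborn-visit and prenatal route puts the survey first, any distortion would be confined to one recruitment route.

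**Working it through.** The protocol states no figure on this point, so the check is a comparison of sequences.

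**Hospital route, as permitted**
1. The mother consents.
2. She may be randomised, since no further condition is stated.
3. The arm is known when the enrollment packet is made up, because the paper screener goes in only for intervention participants who do not sign up for MyGeisinger. Phase One uses the same term, enrollment packet, for the baseline survey itself (Attachment 3). On that reading, the survey and an arm-dependent item travel together.
4. Educational materials, assigned by arm, are given at enrollment.
5. The survey comes back up to one week later if it was not finished in hospital.

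The time and events material in Section 6.5.1 does not prevent this order. It puts the enrollment questionnaires and, for the RCT, the Geisinger/WIC verification that precedes data sharing in the same Day 1-8 window. Section 6.3 keeps Phase One recruitment for the RCT and adds to it, so the hospital route remains in use.

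**Newborn-visit and prenatal route, as written**
1. Consent and completed survey are returned by mail, telephone or REDCap.
2. The participant is enrolled.
3. Care follows the assigned arm.

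The two routes therefore place the survey differently relative to arm-dependent exposure. Only the hospital route allows exposure first.

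**How an error would scale**

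Let *p* be the share of the intervention arm who answer late, *d* the shift in their baseline score caused by early material (in SD, net of any shift in controls), and *r* the correlation between baseline and outcome, with equal SDs.

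- Shift in the arm's mean baseline: *p* × *d*.
- Understatement of a change-score effect, if *d* has the same sign as the intervention effect: *p* × *d*.
- Understatement of a baseline-adjusted effect: *r* × *p* × *d*.

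The protocol gives none of these three quantities. Purely as an assumption, take *d* between 0 and 0.2 SD, *p* between 0 and 0.5, and *r* = 0.5. The change-score error then runs from 0 to 0.5 × 0.2 = 0.1 SD, and the adjusted error from 0 to 0.5 × 0.1 = 0.05 SD. This range only shows how the error scales. It is not an estimate for this trial, and the point does not depend on it.

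**The case against.** The strongest reply is that the text permits this order but does not prescribe it. The survey is meant to be completed during recruitment, and late return is a fallback. Saying that randomisation follows consent fixes an order, not that it happens at once. This is right, and it confines the point to hospital recruits who return the survey late.

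Several stronger readings are tempting, but the protocol does not support them.

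- **The intervention has begun before baseline.** A reader might infer this. The paper screener is a blank clinical questionnaire, given only to intervention mothers not using MyGeisinger. Educational materials go to both arms, and how they differ is not described. The WIC scheduling contact and the nurse call are undated, so contact before the survey is possible but not shown.
- **Feeding intent is a post-randomisation variable.** Attachment 3 is listed by title only, and some parent enrollment measures come from the health record. Whether feeding intent is asked in the enrollment survey is an inference.
- **The primary result is compromised.** The primary endpoint rests on weight-for-age z-scores, with weights extracted from the health record, so it is little affected.
- **The other route already fixes when randomisation is run.** It fixes when enrollment and arm-based care follow, not when the allocation program is run.

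Participants are also stated to be blind to arm. That limits reporting bias, but it does not undo the effect of material already read.

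It can also be said that requiring the survey first loses mothers in a trial that expects 31-33% drop-out. That cost is real. But mothers lost before randomisation do not unbalance the arms, whereas baseline non-return after allocation can.

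What remains is a gap in the order of events. It is a matter of trial procedure, and no later analysis can supply a pre-allocation measurement that was not taken.

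**Conclusion.** The point holds in a limited form. On the in-hospital route, the protocol allows allocation and release of arm-dependent items before the enrollment survey is returned. On the newborn-visit and prenatal route, it puts the completed survey before enrollment and arm-based care. For hospital recruits who return the survey late, baselines for the change, moderator and mediator analyses may be post-allocation. The same applies to initial feeding mode intent if it is collected in that survey.

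The number of such mothers and the size of any distortion cannot be determined from the protocol. The conclusion rests on two readings: that the one-week allowance carries over to the RCT, as the carry-over sentence implies, and that consent alone triggers randomisation on the hospital route. The consequence falls on secondary, survey-based measures. A correction is worthwhile because it is cheap, not because the main comparison is at risk.

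**What to change.** In Section 6.5, Phase Two, state that on every route:

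1. participants are randomised only after signed consent and receipt of the completed enrollment survey, whether on paper, in REDCap or by telephone;
2. arm-dependent items (the paper screener and the arm-based educational materials) and the transfer of the telephone number to WIC follow randomisation, with the paper screener still sent in time for its stated use at the initial WIC visit;
3. the dates of survey completion and of allocation are recorded, and any survey completed after allocation is treated as post-randomisation data.

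This extends to the hospital route, and makes explicit for randomisation itself, the survey-first order that the protocol already uses for newborn-visit and prenatal recruits.

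The cost is protocol wording and one extra mailing. Mothers who take the survey home are allocated up to about a week later. A survey handed over on Day 1 and returned within seven days arrives by Day 8 (1 + 7), still inside the enrollment window of Section 6.5.1. A few consenting mothers who never return the survey will not be randomised; the protocol does not allow their number to be estimated.

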## **Phase Two: Randomized Controlled Trial**

Procedures for Phase Two, Randomized Controlled Trial are the same as those for Phase One, Observational Study except that: 1) participants will be randomized to the treatment or control groups following participant consent/authorization/agreement. An electronic program will be used to randomly assign patients to a group; 2) Pediatric participant data will be extracted from their electronic health records and WIC records to document visit frequency, physical exam, and feeding or nutrition-related metrics 3) Pediatric participants will be given educational materials based on upon their recruitment in the intervention/control arm. These data will be electronically shared between WIC and Geisinger PCPs for the purpose of coordinating care for a 6 month intervention period and then disabled. Geisinger and WIC will share agreed upon data elements using a secure, File Transport Portal (FTP) site daily. Verification of shared participants between GHS and WIC will be authenticated with mother's name, mother's telephone number, date of birth, date of delivery, infant name, and birth date. To increase the likelihood of intervention arm participants enrolling in WIC, the mother's telephone number will be transferred. The telephone number will be used by WIC to contact the participant and schedule an initial visit with a WIC nutritionist in Luzerne County. Following authentication, random participant IDs will be assigned to protect confidentiality; and 3) Participants will be blind to group assignment, however PCPs and WIC will know group assignment because shared data for participants in the treatment group will be electronically displayed in the EHR at Geisinger and the QuikWIC

---

system at WIC for the purpose of coordinating care. A trained research assistant or project coordinator will access the participating patient's medical record for the purposes of creating a documentation encounter in which the data collected from the QuikWIC system will be entered. This data will be stored in EPIC flowsheet rows. The data will then be displayed for the provider in the progress note to assist in the coordination of care. All participants will complete an informed consent form which will include PHI elements being shared. Throughout enrollment in the study, intervention participants will receive a phone call from a trained Geisinger nurse to assist with providing educational guidance for their child (feeding, sleep, tummy time, etc.) We anticipate this call will last around 10 minutes. To best serve the pediatric patient population enrolled in this RCT, the study team will be providing both intervention and control participants with educational materials that were developed in part by the AAP, but also vetted studies which were conducted at The Pennsylvania State University. Educational materials will be distributed to WIC for use during nutrition visits, as well as, provided during enrollment into the study and sent via mail. The purpose of the educational materials is to provide added value to parents enrolled in the study and assist them in providing care for their infant. To ensure participants are able to attend their scheduled WIC nutritionist appointments, the study team will provide a small business-size colored card at enrollment with the WIC contact information to reschedule their appointments if the need arises. The reschedule information is as follows: [name] or Toll free- [name]. In addition, during the 7 month enrollment period, the EHL survey (standard of care) will not fire for control participants, this will be sent via mail included in the 2,5,7 month survey packets. Post-enrollment, the study team will also mail a postcard to participants thanking them for participating in the study and a short high level overview of their participation. The post-card will also serve as a reminder that the participant will be receiving surveys at 3 time points throughout their enrollment. For intervention patients that do not complete the EHL screener at their regularly scheduled WCV, the study team will send a mailed copy of the EHL survey to the home for the parent to complete. To ensure that intervention participants are presented the opportunity to complete the EHL screener, the study team will include a paper copy of the screener in the participant's enrollment packet. The survey will only be included should the participant choose not to sign-up for MyGeisinger and prefer to complete the survey on paper Enrollment in MyGeisinger is not an inclusion/exclusion criteria. For participants that are given the EHL screener at enrollment, once the screener is completed at home, the participant will be asked if they could please bring the survey with them to their initial WIC visit. The screener will be used to better inform the WIC nutritionist visit and does not contain PHI. The screener will then be collected by the WIC nutritionist and transferred electronically back to Geisinger study staff. This data is essential in comparing intervention and control participants. To ensure that our participants are able to receive their survey packets in a timely manner, whether by mail or email as indicated by the participant, a study staff member will contact the participant via phone call. This phone call will consist of confirmation of receipt of survey, and to allow the participant to ask any questions that have arisen through the process of reading the questionnaire and answering the questions to the best of their ability. If the study team is unable to reach the participant via phone, a voicemail will be left asking the participant to call the study team back if they did not receive their survey. Participants will also receive an

---

email or mailed reminder which includes the survey to complete should it not be returned within a timely manner. The mailed reminder will be sent to the participant with a self-addressed stamped envelope in which to return the survey. The participant is not required to return the re-mailed survey if they have completed the initial copy which was sent. Once the survey is received from the participant, a \$50 will be sent thanking them for their time and participation. Information collected in the study surveys is time sensitive and directly related to the child's age at the 2,5,7 month time periods, thus it is important to receive the data in a timely manner. No data will be shared between WIC or PSU (as indicated in the above observational study) until an informed consent form is completed and the participant understands their role in the study and what will be shared.

The study team also plans pursue recruitment of eligible pediatric patients at newborn visits in participating Partners in Pediatrics clinics. Due to the nature of recruitment in a labor and delivery environment, it is not always possible to capture all eligible participants, which introduces bias, and more than a third of the potential participants pre-screened are ineligible due to a non-participating pediatrician, and nearly a third of potential participants that receive direct recruitment are also not eligible due to a non-participating pediatrician. By instituting recruitment prior to delivery and at the newborn visit with participating pediatricians, the study team hopes to equitably capture the largest eligible population. To achieve this goal, the study team will provide WIC and Partners in Pediatrics sites with a study flyer, WIC income eligibility flyer, and a short information sheet to provide to eligible participants. The approved prenatal recruitment flyer will also be distributed via social media. A data analyst in the Obesity Institute will pull a recruitment list that screens all Geisinger patient-participants for eligibility and provide this to the study team daily. A research assistant on the project will then screen the patient's medical record via chart review to ensure all inclusion criteria are met and there are no additional exclusions (adoption, drug use, etc.). For patients screened as eligible, the study team would contact the regional director for pediatrics who would notify clinic staff to distribute materials at the 3-5-day newborn visit. For prenatal recruitment of non-Geisinger patients, interested participants will contact the study team. Afterwards, the study team will follow-up via phone (mobile or home) or email or mail to arrange to or discuss the study with the potential participant. If interested, the study team will then send two copies of the consent form, the enrollment survey, a pre-paid stamped envelope, and instructions on how to complete and return the consent form and survey. During the course of the phone call, should the participant elect to complete the enrollment survey via over the phone, the study staff member will record the survey responses utilizing the RedCap system which stores all participant survey results. In addition, the participant may also elect to receive the consent form and survey electronically via RedCap, during their conversation with the research assistant. If the participant chooses to receive the e-consent, an electronic version of the WEE consent form and enrollment survey will be send to the participant's email that they provide on the phone. The consent will be emailed and stored securely in the RedCap system, which is only accessible to approved GHS study team members. If the participant does not complete the e-consent in a timely fashion, the RedCap system will send automated reminders. Once the participant returns the consent form or e-consent form and

---

completed survey, they will be enrolled into the study and care will resume as noted above based upon whether the participant is randomized to the intervention or control arm.

To ensure providers are effectively utilizing the coordination of care display module that was built within EPIC, the study team plans to conduct physician shadowing at participating clinics in Luzerne County. This will include shadowing providers, ensuring the IT module is working as intended, and to provide any oversight/problem solving that is necessary. The study team will also use this opportunity to discuss physician satisfaction with the end product and improvements/modifications that should be made to improve efficiency and assist with current workloads.

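### EHL data are called essential for comparing the arms but are collected by different routes in each arm, so any EHL difference is partly confounded with mode, setting and audience

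*Protocol*

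**What the plan says.** The rules are in Section 6.5, Phase Two.

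- **Controls.** During the 7 month enrollment period the EHL survey "will not fire for control participants, this will be sent via mail included in the 2,5,7 month survey packets". No EHL form at enrollment is described for this arm.
- **Intervention, default route.** The screener is expected at the regular well child visit.
- **Intervention, fallback.** If a mother has not filled it in there, "the study team will send a mailed copy of the EHL survey to the home for the parent to complete".
- **Intervention, enrollment paper copy.** A paper screener goes into the enrollment packet, with a limit: "The survey will only be included should the participant choose not to sign-up for MyGeisinger and prefer to complete the survey on paper". For these mothers, "once the screener is completed at home, the participant will be asked if they could please bring the survey" to the first WIC visit. The nutritionist uses the answers in that visit and sends the form back to study staff.

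Directly after this comes the statement on purpose: "This data is essential in comparing intervention and control participants".

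Two other places describe EHL differently. The Abstract (Section 2) says both Phase Two groups are exposed to EHL screening, and that it is a clinical tool rather than a study questionnaire. Section 6.5.1 carries the Phase One schedule into Phase Two. That schedule marks EHL at Day 1-8 and Months 2, 5 and 7, and none of the listed Phase Two exceptions concerns EHL or separates the arms.

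**The concern.** A between-arm comparison of a self-reported instrument is interpretable when both arms complete it under the same conditions. Here assignment determines the default conditions. An intervention mother normally completes the form in connection with a clinical visit, or hands it to the person about to counsel her. A control completes it at home as part of a research mailing. Mothers may answer feeding questions differently depending on where they answer and who will read the form, and who responds at all may also differ between a visit and a mailing. An observed EHL difference could then come from the intervention, from the collection route, or from both, and the data would not separate them.

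This cannot be left to the analysis, because it is a collection rule. Once the forms have been gathered by different routes, no model can recover what controls would have answered at a visit.

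**Working it through.** The plan states no figure for an EHL comparison, so there is nothing to reproduce. The check sets the routes side by side and then illustrates sensitivity.

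**1. Routes by arm (Section 6.5, Phase Two)**

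| Feature | Intervention | Control |
|---|---|---|
| Default route | Well child visit | Mailed packet |
| Mailed to home | Only if not completed at the visit | Always |
| Enrollment form | Paper copy for mothers who do not join MyGeisinger and prefer paper | None described |
| Use of answers in counselling | Described for the form handed in at WIC | None described |
| Timing stated | Visit schedule (ages not given), plus enrollment for some | 2, 5 and 7 months |

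The routes overlap only where intervention mothers complete the form at home. The overlap is real, so the confounding is partial.

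**2. Can adjustment for mode repair it?** No control form is collected at a visit, so there is no contrast between arms within that mode. Within the mailed mode, all controls would be compared with the intervention mothers who did not complete the screener at the visit. Within home-completed paper, the intervention mothers are those who declined MyGeisinger and chose paper. Both are subsets selected by the mother's own behaviour after randomization, so neither stratum is a randomized comparison.

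**3. Enrollment.** The sentence calling the data essential follows the description of the enrollment form handed in at WIC. Section 6.5 describes no control form at that age; the first control EHL comes with the 2 month packet. Section 6.5.1 marks EHL at Day 1-8 without distinguishing the arms. The two sections do not agree.

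**4. Sensitivity (assumed values only).** Let m be the shift in SD units caused by visit-type rather than mailed completion, and p the share of intervention screeners completed that way; for controls the share is 0. The spurious arm difference is b = m × (p − 0) = m × p. Neither m nor p is in the documents.

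Number per arm: 350 pairs (Section 6.2.1) × 0.67 retained (Section 6.6.2) / 2 = 117.25, taken as 117. The standard error of a difference in means with SD 1 is √(2/117) = 0.131. With no true effect, the two-sided 5% rejection rate is Φ(b/0.131 − 1.96) + Φ(−b/0.131 − 1.96).

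| m (SD) | p | b (SD) | Rejection rate |
|---|---|---|---|
| 0.1 | 0.5 | 0.05 | 0.067 |
| 0.1 | 1.0 | 0.10 | 0.119 |
| 0.2 | 0.5 | 0.10 | 0.119 |
| 0.2 | 1.0 | 0.20 | 0.334 |
| 0.3 | 0.5 | 0.15 | 0.209 |
| 0.3 | 1.0 | 0.30 | 0.631 |

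If p were 0, with every intervention screener collected by mail, b would be 0 and the rate 0.05. The table shows how the error rate depends on two unknowns. It does not estimate the bias in this trial.

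**The case against.** The best case on the other side has four parts.

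*The modes overlap.* Intervention mothers who miss the screener at the visit get it by mail, as controls do. The WIC-route form is completed at home; WIC collects and uses it. The MyGeisinger wording also suggests that some completion may be through the portal. This stands. A reader might infer that every EHL difference is wholly an artefact of mode; the text does not support that.

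*Timing may be the same.* Section 6.5 gives no ages for the well child visits, and Section 6.5.1 lists one EHL schedule. This stands in part. Different timing is a possibility, clear only for the enrollment paper form, which has no described control counterpart.

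*EHL is not an outcome.* The primary endpoint is weight-for-age z-score, EHL is not listed among the secondary endpoints, and the Abstract says it is not a study questionnaire. This stands and limits the consequence. The Secondary Endpoints text refers to boxes in a figure that is not shown, so whether EHL items feed any of those measures cannot be settled. It does not remove the point, because the protocol itself assigns these data to the arm comparison.

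*The sentence may only explain why the WIC-collected form must be returned.* That reading is possible. Even so, the stated reason for wanting the form back is to compare arms, and that is the form without a described control counterpart.

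Two further inferences are tempting and unsupported. One is that the bias must favour the intervention: nothing in the documents fixes its direction, Section 6.5 says participants are blind to assignment, and a form completed before the first WIC visit precedes that visit's counselling. The other is that controls have a payment incentive that intervention mothers lack: the gift cards are tied to the survey packets without restriction by arm, and no card is said to depend on the EHL form.

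**Conclusion.** The point holds in a limited form. Section 6.5 assigns EHL data to the comparison of arms while fixing different default collection routes for each, so an EHL difference would be partly confounded with mode, setting and audience, and possibly timing. Adjustment for mode would not restore the randomized comparison.

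The size and direction of the bias cannot be derived from the documents. Under assumed mode effects of 0.1 to 0.3 SD, and with 50% to 100% of intervention screeners completed at visits, a nominal 5% test with 117 per arm would reject about 7% to 63% of the time without any true effect. That range reflects the assumptions and should not be used to grade the problem.

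The primary weight outcome is not affected, and EHL is not a named endpoint. This is an inexpensive improvement to the plan and gives no reason to doubt the main result. Separately, Section 6.5 does not agree with the Abstract or with Section 6.5.1 on who receives EHL, when, and for what purpose.

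**What to change.** 1. Include the same EHL items in the existing 2, 5 and 7 month packets for both arms, with the same instructions, reminders and return route.
2. State that any between-arm comparison of EHL uses only those packet responses.
3. Use screeners completed at well child visits or handed in at WIC only to describe how the intervention was delivered.
4. Correct the sentence that calls the WIC-collected data essential for comparing the arms, so that it matches items 2 and 3.
5. Reconcile Section 6.5 with the Abstract (both groups exposed; not a study questionnaire) and with Section 6.5.1 (one EHL schedule for Phase Two, including Day 1-8). Clinical use of the screener is for the sponsor to settle; items 1 to 4 do not depend on it.

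The cost is wording changes and one extra short form in each intervention packet. Some intervention mothers will answer similar questions twice, a slight added burden.
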